9 COMPUTER SOFTWARE

All analyses will be performed by BTG using Version 9.4 or later of SAS® software. All summary tables and data listings will be prepared utilizing SAS® software.

11 APPENDICES

11.1 APPENDIX 1: VARIABLE DEFINITIONS

Age will be calculated as follows

$$\text{Age} = (\text{Cryoprocedure Date} - \text{Date of birth})/365.25.$$

Only the integer part of the result will be taken.

11.2 APPENDIX 2: STATISTICAL ANALYSIS AND PROGRAMMING DETAILS

The SAS procedure LIFETEST will be used in the Kaplan-Meier analyses. Patients who did not have an event will be censored.

Example code is as follows:

```
proc lifetest data=all method=km alpha=0.05 outsurv=interval;  
  time aval*censr(1);  
  id usbjid;  
run;
```

The SAS procedure PHREG will be used in the Cox regression analysis of time-to-event endpoints. Patients who did not have an event will be censored. The SAS method of discrete will be used to handle ties.

Example code is as follows:

```
proc phreg data=all;  
  model aval*censr(0) = &covar /ties=discrete rl alpha=0.05;  
run;
```

**12 TABLE, LISTING, AND FIGURE SHELLS WILL BE PROVIDED AS A
SEPARATE DOCUMENT.**

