6.4.4 Disease recurrence

Time to recurrence (TTR) is defined as the time from date of cryoprocedure to disease recurrence with enhancement in at least one lesion. A lesion is considered to have disease recurrence if the response to the question “What is the status of the lesion?” in the follow-up lesion assessment eCRF page, is “Recurrent”, and there is a “Yes” response to the related question, “If Progressing or recurrent, was the lesion identified by contrast enhancement?”

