6.4.5 Disease-specific survival

Disease-specific survival (DSS) is defined as the time from date of cryoprocedure until date of death due to kidney cancer. Deaths due to kidney cancer will be identified by a manual review, performed by Galil Medical, of the causes of death recorded in the study database.

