8.6.6.1 Time to Recurrence (TTR)

TTR will be computed as

$$\text{TTR (Months)} = (\text{Date of event/censor} - \text{Date of cryoprocedure} + 1) / 30.4375.$$

Censoring will be performed in the following order:

- 1) If a patient does not have a baseline lesion assessment, then the TTR time will be censored at the date of cryoprocedure, regardless of whether or not recurrence was observed after treatment.
- 2) If a patient has recurrence but has two or more missing lesion assessment visits (according to the 6 to 60 month analysis visits in Section 6.2.2) immediately before recurrence was observed, the TTR time will be censored at the date of the post treatment lesion assessment that occurred immediately before the first of the missed visits. For example, if a patient had a lesion assessment at Month 6, but did not have an assessment at Months 12 and 24, and then had recurrence at the Month 36 assessment, then the TTR time would be censored at the date of the Month 6 assessment.
- 3) If a patient is known not to have recurrence, the TTR time will be censored at the last date of lesion assessment date, or at the date of cryoprocedure if the patient does not have any post-treatment lesion assessments.

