8.6.6.2 Disease-specific Survival (DSS)

DSS will be computed as

$$\text{DSS (Months)} = (\text{Date of event/censor} - \text{Date of cryoprocedure} + 1) / 30.4375.$$

For each patient that has not died due to kidney cancer, DSS will be censored at the date of death due to other causes or at the date last known to be alive as recorded on the eCRF.

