8.6.6.3 Overall survival

OS will be computed as

$$\text{OS (Months)} = (\text{Date of death/censor} - \text{Date of cryoprocedure} + 1) / 30.4375.$$

For each patient that has not known to have died, OS will be censored at the date last known to be alive as recorded on the eCRF.

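### The SAP's example code gives one undefined censoring flag opposite meanings in the Kaplan-Meier and Cox blocks, so one block, if run as written, analyses time to censoring; separately, `age*10` is not a 10-year scale

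*SAP*

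**What the plan says.** SAP Section 11.2 puts the same sentence before each code block: "Patients who did not have an event will be censored". The blocks then read:

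- PROC LIFETEST, on dataset `all`: "time aval*censr(1" and a closing bracket.
- PROC PHREG, also on dataset `all`: "model aval*censr(0) = &covar /ties=discrete rl alpha=0.05".

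No recoding step stands between them. Section 11.1, the appendix for variable definitions, defines only age, in whole years. `censr` is defined nowhere in the SAP.

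The endpoint rules in the body are clear:

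- Time to recurrence (TTR), Section 6.4.4: "Time to recurrence (TTR) is defined as the time from date of cryoprocedure to disease recurrence with enhancement in at least one lesion". Under Section 8.6.6.1 a patient without recurrence is censored at the last lesion assessment, "or at the date of cryoprocedure if the patient does not have any post-treatment lesion assessments".
- Disease-specific survival (DSS), Section 8.6.6.2: "For each patient that has not died due to kidney cancer, DSS will be censored at the date of death due to other causes". Survivors' times stop when they were last confirmed living.
- Overall survival (OS), Section 8.6.6.3: for patients not known to have died, "OS will be censored at the date last known to be alive as recorded on the eCRF".

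On the separate point, Section 7.2 enters age as a continuous covariate scaled as `age*10`, with the stated aim of a 10-year risk, in both the Cox list and the logistic list for adverse events.

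**The concern.** In both procedures the bracketed value after the status variable is the one treated as censored. The two blocks therefore give the same flag opposite meanings. Whichever coding is used, one block treats events as censored and censored patients as events.

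What is at stake depends on the block:

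- **If PHREG is the wrong block**, the univariable Cox models for TTR, DSS and OS, and the p<0.15 screen into the multivariable model, describe the hazard of being censored. For DSS, deaths from other causes would count as events.
- **If LIFETEST is the wrong block**, the 6- to 60-month rates, quartiles and curves describe time to censoring. For TTR, patients with no baseline or no post-treatment lesion assessment are censored at the procedure date. The +1 in the formula gives them a positive time, so they would appear as events on day 1.

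The logistic models for adverse events do not use the flag. The age scaling changes only the printed age ratio and its interval.

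**Working it through.** **1. Logic of the two blocks.** Let e = 1 for an event and 0 otherwise.

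| Coding of `censr` | LIFETEST (1 = censored) | PHREG (0 = censored) |
|---|---|---|
| 1 = censored (`censr` = 1 − e) | right | swapped |
| 1 = event (`censr` = e) | swapped | right |

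Exactly one block is swapped in each row. The plan gives no definition with which to choose the row.

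**2. Inputs for size.** From the documents: n of about 250 (SAP Section 4.4). Assumed, because the documents give no figures: 5-year event risk 5% to 20% (10% as the central case), 5-year dropout 20% or 50%, exponential times, a balanced binary factor with a true hazard ratio of 2.0, and follow-up ending uniformly over 54–66 or 60–66 months. The plan states no figure of its own to reproduce.

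**3. Swapped Cox model** (1,000 simulated datasets per scenario, dropout unrelated to the factor). Correct coding gives a median hazard ratio of 1.90 to 2.08 over all scenarios; swapped coding gives 0.99 to 1.01. This is not the reciprocal, which would be 0.50. At 10% risk the factor passes p<0.15 in 49% to 56% of datasets when correctly coded and in 15% to 16% when swapped, which is about the rate for a factor with no effect. A separate simulation (10% risk in the reference group, censoring uniform on 6–90 months and capped at 66) gives 1.94 correct and 1.00 swapped.

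**4. Swapped Kaplan-Meier, general form.** The curve estimates the share not yet censored: (1 − dropout)^(t/60) × P(follow-up ends after t). The first figure is for 20% dropout, the second for 50%.

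- 24 months: 0.80^0.4 = 0.915; 0.50^0.4 = 0.758.
- 48 months: 0.80^0.8 = 0.837; 0.50^0.8 = 0.574.
- 60 months, follow-up ending at 54–66: 0.80 × 0.50 = 0.40; 0.50 × 0.50 = 0.25.
- 60 months, no follow-up ending before month 60: 0.80; 0.50.

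At 10% risk the true rates are 0.90^0.4 = 0.959, 0.90^0.8 = 0.919 and 0.90. The 60-month result depends heavily on when follow-up is assumed to end. For OS and DSS that pattern is purely an assumption: the 60-month visit window in SAP Section 6.2.2 assigns assessments to visits, while these endpoints are censored at last known alive.

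**5. Swapped Kaplan-Meier for TTR** (300 datasets per scenario, 10% risk, assessments at 6, 12, 24, 36, 48 and 60 months ± 3, censoring at last assessment, 0% to 10% of patients with no post-treatment assessment).

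| | 24 months | 60 months |
|---|---|---|
| True rate | 95.9% | 90% |
| Correctly coded, detected at visits | about 97% | about 90% |
| Swapped, 20% dropout | 80% to 89% | 36% to 41% |
| Swapped, 50% dropout | 63% to 70% | 22% to 25% |

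The correct estimate lies slightly above the true rate at 24 months because recurrence is seen only at a visit. The swapped curve starts with a day-1 step of 2% to 16%.

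**6. Event counts.** Correct coding gives about 9 to 47 events across the Cox and Kaplan-Meier scenarios. Swapping gives 250 − 47 = 203 to 250 − 9 = 241.

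**7. Age.** One unit of `age*10` is 0.1 year, so the printed ratio is (10-year ratio)^(1/100). Assumed 10-year ratios of 1.2, 1.5, 2.0 and 3.0 print as 1.002, 1.004, 1.007 and 1.011. A linear rescaling leaves the p-value and the p<0.15 screen unchanged.

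**The case against.** The code is labelled as an example and looks like a template: a generic dataset name, an unfilled macro for the covariate and a misspelled identifier. The governing prose, before each block and in Sections 8.6.6.1 to 8.6.6.3, is correct. The conflict does harm only if a block is used unchanged. That stands, and it makes the finding conditional.

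A swap would also be conspicuous, with more than 200 events where a few dozen at most are expected. Section 8.1 plans a table of censored patients with reasons, which needs more than a 0/1 flag. Section 5.2 records that the Steering Committee had reviewed draft outputs dated 08 May 2018 and changed the TTR event as a result. This makes an undetected swap less likely but does not rule it out. Section 8.1 does not say how its counts are derived, and a swapped Cox model prints unremarkable ratios near 1. The SAP also says that the study is not powered for formal analysis, so the Cox screens are exploratory. The Kaplan-Meier rates, however, are main long-term results of the registry.

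A reader might infer that the registry's reported results are wrong, or that the Cox block is the faulty one. The documents support neither: they do not show the production programs, and without a definition of `censr` nothing identifies the wrong block.

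**Conclusion.** The point holds as a conditional error in the written specification. The contradiction is certain from the text. Its effect on any result is not, because it arises only if the wrong block is run as written.

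If it does arise, the effect is large: a true hazard ratio of 2.0 prints near 1.0 when dropout is unrelated to the factor, and the TTR rates fall to the swapped ranges in the table above. All inputs except n of about 250 are assumptions, so these figures show the order of the error and do not predict the registry's results.

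The age scaling is a separate and minor slip. It contradicts its own stated purpose but affects only how one ratio is printed. A reader might infer that it distorts covariate selection; it does not.

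**What to change.** 1. Define `censr` once in SAP Section 11.1, and use the same censored value in LIFETEST and PHREG.
2. For TTR, DSS and OS, compare the event and censored counts printed by each procedure with counts taken directly from source, after applying the censoring rules of Sections 8.6.6.1 to 8.6.6.3. The sources are eCRF death records for OS, the reviewed causes of death for DSS ("identified by a manual review, performed by Galil Medical, of the causes of death recorded in the study database"), and lesion status recurrent with enhancement confirmed for TTR. A table built from `censr` would inherit the error and cannot serve as the check.
3. Replace `age*10` with `age/10` in both covariate lists of Section 7.2.

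The cost is one definition, one changed code value, one count check on three endpoints from fields already collected, and two edits to the covariate lists. The one risk is aligning both procedures to the wrong value, which the source-count check would reveal.

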4.4 Determination of Sample Size

Approximately 250 patients are expected to participate in TRACE. As the registry is an observational, non-comparative study, power calculations have not been performed. The estimated sample size has been established to help ensure an adequate population of “completed patients,” defined as those patients completing four or more years of follow-up, at the closure of the registry. This study is not powered for formal statistical analysis.

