7 STATISTICAL METHODS

7.1 General Methodology

All statistical tests will be two-sided with a significance level of $\alpha=0.05$, unless specified otherwise, and will be performed using SAS[®] Version 9.4 or later. Data will be summarized

using descriptive statistics (number of patients [n], mean, standard deviation [sd], median, interquartile range, minimum, and maximum) for continuous variables and using frequency and percentage for discrete variables.

Patient listings of all data from the case report forms (eCRF) as well as any derived variables will be presented.

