7.2 Adjustments for Covariates

The following covariates will be included, one at a time, in ‘univariable’ Cox regression analysis of time-to-event efficacy endpoints.

- Age (continuous as age*10 to assess 10 year risk)
- Gender
- Race
- Maximum lesion size (≤ 4 cm, > 4 cm) at baseline using the greatest trans-axial diameter
- Number of cryosurgery needles used
- Type of needles used
 - Needles with the cautery feature (IceRod CX, IceFORCE 2.1 CX, IcePearl 2.1 CX) vs other types; a patient is deemed to be in the ‘Needles with the cautery feature’ group if any needle used in that patient was of that type
- Duration (in months) from date of initial diagnosis of the suspicious renal mass to cryoprocedure (continuous variable)
- Baseline eGFR (continuous variable)
- Histological type (conventional renal cell carcinoma [RCC] versus other)
- BMI (continuous variable)
- ASA classification
- NS complexity category at baseline (low, moderate, high) (as defined in Section 6.3)
- Cryoprocedure surgical approach
 - Note: there is only one patient with an open procedure, so only laparoscopic and percutaneous procedures will be included in this analysis
- Prior renal surgery
- Prior abdominal surgery
- Solitary kidney (yes versus no); a patient is considered to have a ‘yes’ for this variable if ‘Nephrectomy’ is selected on the Medical History eCRF page.
- History of hypertension
- History of diabetes
- Use of anticoagulants

All factors in the univariable models with a two-sided p-value < 0.15 will be included in a multivariable analysis to determine the impact of these factors.

The following covariates will be included, one at a time, in ‘univariable’ logistic regression analysis of the occurrence of an adverse event (AE).

- Age (continuous as age*10 to assess 10 year risk)
- Gender
- Race
- Maximum lesion size (≤ 4 cm, > 4 cm) at baseline using the greatest trans-axial diameter
- Number of cryosurgery needles used
- Type of needles used
 - Needles with the cautery feature (IceRod CX, IceFORCE 2.1 CX, IcePearl 2.1 CX) vs other types; a patient is deemed to be in the ‘Needles with the cautery feature’ group if any needle used in that patient was of that type
- Histological type (conventional renal cell carcinoma [RCC] versus other)
- BMI (continuous variable)
- ASA classification
- NS complexity category at baseline (low, moderate, high) (as defined in Section 6.3)
- Cryoprocedure surgical approach

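### The Cox screen names no test and has no rule for few events; if all events fall in one level of a factor, the Appendix 2 code gives an infinite hazard ratio, and a Wald-based screen could drop a strong factor

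*SAP*

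**What the plan says.** SAP 7.2 lists 19 covariates, to be entered one at a time in a "Cox regression analysis of time-to-event efficacy endpoints". Those endpoints are time to recurrence (TTR), DSS and overall survival (OS). The selection rule is: "All factors in the univariable models with a two-sided p-value < 0.15 will be included in a multivariable analysis". The section does not say whether that p-value is Wald, score or likelihood ratio. It sets no minimum number of events, no limit on the size of the multivariable model, and no action if a model fails to converge. Its one sparse-data step is to leave the single open-procedure patient out of the comparison of surgical approaches.

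SAP Appendix 2 (11.2) introduces its code with "Example code is as follows" and gives one PHREG statement: "model aval*censr(0) = &covar /ties=discrete rl alpha=0.05". It requests neither a penalty nor profile-likelihood limits. That `rl` alone yields Wald limits is a software default, not something the SAP states.

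On the number of events, SAP 4.4 says "Approximately 250 patients are expected to participate in TRACE" and "power calculations have not been performed". For DSS only kidney-cancer deaths count: "For each patient that has not died due to kidney cancer, DSS will be censored at the date of death due to other causes" (SAP 8.6.6.2). Protocol 6.3 excludes metastatic disease. Protocol 6.4 describes the typical lesion as 4 cm or less, and Protocol 6.2 requires only a suspicious lesion. Neither document gives an expected or observed count for any of the three endpoints.

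**The concern.** Most of the 19 covariates are categorical. When every event falls in one level of such a factor, the partial likelihood keeps rising as the log HR grows. The estimate runs to infinity and its standard error grows faster still. The Wald statistic then goes to zero, its p-value to 1, and the interval covers everything. This is a failure of the Wald approximation, not evidence that the factor is unimportant.

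Two things are at stake, most plausibly for DSS. First, the HR and limits from the specified code cannot be used for such a factor, whichever test did the screening. Second, the set of factors carried into the multivariable model depends on a choice the SAP leaves open.

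**Working it through.** The plan gives no event count or power figure, so there is nothing to reproduce. The check asks what the specified fit does when events are few.

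**Inputs.** From the SAP: about 250 patients (4.4), 19 covariates and a threshold of 0.15 (7.2), unpenalised Cox (11.2). Assumed, because the documents are silent: number of events D, share q of patients in the factor level, and true HR. I also assume the censoring indicator is coded correctly in the Cox fit. The LIFETEST and PHREG examples use different censoring values, 1 and 0, which needs reconciling separately.

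**Formulas.** Holding the composition of the risk set constant, each event falls in the level with probability π = q·HR / (q·HR + 1 − q). With k of D events in the level:

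- log HR = ln[k/(D−k)] − ln[q/(1−q)], with SE = √[1/k + 1/(D−k)]; Wald p comes from their ratio
- LR = 2{k ln[(k/D)/q] + (D−k) ln[((D−k)/D)/(1−q)]}, on 1 degree of freedom

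**Step 1: D = 5, q = 0.5.**

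| Split | Wald p | Likelihood-ratio p |
|---|---|---|
| 3:2 | 0.66 | 0.65 |
| 4:1 | log HR = ln 4 = 1.386, SE = √1.25 = 1.118, p = 0.215 | LR = 1.93, p = 0.165 |
| 5:0 | near 1 | LR = 10 ln 2 = 6.93, p = 0.0085 |

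No split passes a Wald screen at 0.15. Only 5:0 (or 0:5) passes a likelihood-ratio screen. The Firth penalised p for 5:0 is 0.027, which also passes. At HR 8, π = 8/9 and P(5:0) = (8/9)^5 = 0.55. The chance of passing is therefore 0% by Wald and 55% by likelihood ratio or Firth.

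**Step 2: full Cox fits, N = 250, all events in one level.** For D = 2 to 12 and q = 10% to 90%, the Wald p was 0.991 to 0.998 every time, with an SE of about 1,600 to 7,600. With 5 events in a 20% level:

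- Ordinary fit: log HR 19.3, SE about 3,600, Wald p 0.996
- Score and unpenalised likelihood-ratio p: about 0.0001 or less
- Firth with profile limits: HR about 40 (95% limits about 4.5 to 5,250), p = 0.0002

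**Step 3: chance of passing p<0.15 across settings.** The first three rows simulate full Cox data with approximate event counts; the rest use the formulas above.

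| Events | q | HR | Wald | Likelihood ratio |
|---|---|---|---|---|
| 3 | 20% | 20 | 26% | 86% |
| 5 | 20% | 10 | 61% | 82% |
| 20 | 20% | 10 | 99% | 100% |
| 10 | 50% | 8 | 60% | 91% |
| 10 | 20% | 3 | 69% | 69% |
| 10 | 35% | 2 | 43% | 43% |
| 20 | 50% | 8 | 90% | 99.6% |
| 20 | 90% | 8 | 0% | 76% |

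The loss ranges from nothing to large. By 20 events it is about 10 points or less, except in the 90% level.

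**Step 4: separation is not always strong evidence.** With all 5 events in a 90% level, LR = 10 ln(1/0.9) = 1.05, so p = 0.30, and the Firth p is 0.89. The full Cox fit gives score 0.36, likelihood ratio 0.22 and Firth 0.66. The factor fails at 0.15 under every test, and that is reasonable.

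**The case against.** A reader might infer that the plan, as written, screens out the strongest predictor. The documents do not support that. SAP 7.2 names no test, the Appendix 2 line is example code, and `rl` concerns confidence limits rather than selection. A score or ordinary likelihood-ratio p-value would usually keep a strong factor with no penalty at all. Nor is a factor that holds every event necessarily the strongest: step 4 shows the contrary for a common level.

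It can also be said that few events is an inference; that no count is shown for TTR or OS; that many realistic settings show no loss; and that Firth adds little over the likelihood ratio for selection. All of this stands. With 10 events, a 90% level and HR 8, Firth passes 0% and the likelihood ratio 87%. Standard errors in the thousands would alert an analyst, SAP 4.4 disclaims formal power, and the Kaplan-Meier reporting of DSS is untouched. Firth limits of 4.5 to 5,250 hardly settle a risk-factor question.

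A further tempting step is to extend the point to the adverse-event logistic models in 7.2. Nothing in the documents shows that any-adverse-event occurrence is sparse, and Appendix 2 has no logistic code, so that extension is not made.

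What survives: a better screening test repairs selection only. Under separation the specified code still reports an infinite HR with uninformative limits, and the SAP has no rule for that case.

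**Conclusion.** The concern holds in conditional form. The SAP leaves the screening test unnamed, has no sparse-event rule, and specifies a Cox fit that breaks down when one level holds every event. If the Wald p-value is used, the cost can be complete (0% versus 55% at 5 events, 50% prevalence, HR 8) or nil (69% either way at 10 events, 20% prevalence, HR 3).

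These sizes rest on assumed event counts, prevalences and HRs and, for the enumerated figures, a constant risk set. Few DSS events is plausible from the eligibility criteria and typical lesion size, but it is not documented. No primary estimate changes; what is at risk is the risk-factor analysis for DSS, and for any other endpoint that turns out sparse. The change should be made, as a modest one.

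**What to change.** - **SAP 7.2:** state that the Cox screen at 0.15 uses the likelihood-ratio (or penalised likelihood-ratio) p-value, not Wald.
- **SAP Appendix 2:** for endpoints with few events, by a threshold written into the SAP, or when the likelihood is monotone, report Firth-penalised HRs with profile-likelihood limits. Use Efron ties for those fits; the discrete method can stay elsewhere.
- **SAP 7.2:** limit the parameters in each multivariable Cox model by the observed events, using a numeric rule (one parameter per m events, with m stated). Fit no multivariable DSS model when there are fewer than 2m events.

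The cost is a few code options and a few sentences. The downsides are slight shrinkage, intervals that remain wide, and possibly no multivariable DSS model. The unpenalised likelihood ratio is also somewhat liberal with few events: in the simulations with no effect and 20% prevalence, it passed 19% at about 5 events and 22% at about 8, against 9% and 11% for Firth. That is tolerable in a screen, but the choice should be recorded.
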